5. TREATMENT ALLOCATION AND BLINDING

Treatment Allocation

Procedures for Randomization

Central randomization will be implemented in this study. In the main study, subjects will be randomly assigned to 1 of 3 treatment groups based on a computer-generated randomization schedule prepared before the study by or under the supervision of the sponsor. The randomization will be balanced by using randomly permuted blocks and stratified by region. Similarly, subjects eligible for the late boost vaccination will be randomly (3:1 ratio) assigned to active vaccine or placebo. The randomization will be balanced by using randomly permuted blocks and stratified by region (USA, East Africa: assuming sufficient numbers from Rwanda in the LTE phase) and by group randomized to in the main study (Group 1/Group 2).

The interactive web response system (IWRS) will assign a unique treatment code, which will dictate the treatment assignment and matching study vaccine for the subject. The requestor must use his or her own user identification and personal identification number when contacting the IWRS, and will then give the relevant subject details to uniquely identify the subject.

Blinding

The subjects, study-site personnel (except for those with primary responsibility for study vaccine preparation and dispensing), and investigator will be blinded to study vaccine allocation of the main study until Week 72, with the exception of the partial unblinding for the start of the LTE phase (see below). The sponsor will be blinded to study vaccine allocation until the primary (Week 28) analysis (see Section 11.6).

The pharmacist with primary responsibility for vaccine preparation (see Section 14.3) will not be blinded to the study vaccine. In order to preserve blinding, he/she will place an overlay on the syringes. Administration of study vaccine to the subjects can be performed by a qualified healthcare provider from the study site (including the pharmacist who prepared the study vaccine) who will have, on the day of administration, no other study function related to safety, study data evaluation or recording of AEs for those subjects that he/she vaccinated on that day.

The investigator will not be provided with randomization codes. The codes will be maintained within the IWRS, which has the functionality to allow the investigator to break the blind for an individual subject.

Data that may potentially unblind the treatment assignment will be handled with special care to ensure that the integrity of the blind is maintained and the potential for bias is minimized. This can include making special provisions, such as segregating the data in question from view by the investigators, clinical team, or others as appropriate until the time of database lock and unblinding.

Under normal circumstances, the blind to study vaccine allocation of the main study should not be broken by the investigator until the end of the main study and the Week 72 electronic data capture (eDC) database is finalized for the subjects, study-site personnel (except for those with primary responsibility for study vaccine preparation and dispensing), and investigator. However, for the purpose of the LTE phase, the investigator, the study-site personnel, and the subject will be informed if the subject qualifies for the LTE phase (ie, subject is randomized to Group 1 or Group 2: qualifies, subject is randomized to Group 3: does not qualify) when the subject reaches the Week 72 visit, or as soon as possible following Week 72 upon sponsor unblinding at the Week 28 analysis. This will result in the partial unblinding of the investigator, the study-site personnel, and the subjects, as they will be informed if the subject qualifies for the LTE phase but will not be informed which qualifying group the subject was randomized to.

The subjects, study-site personnel (except for those with primary responsibility for study vaccine preparation and dispensing), and investigator will be blinded to study vaccine allocation of the late boost vaccination until the subject's last visit. The sponsor will be blinded until the interim data analysis approximately 4 weeks after the last subject received the late boost vaccination.

The investigator may in an emergency determine the identity of the treatment by contacting the IWRS. While the responsibility to break the code in emergency situations resides solely with the investigator, it is recommended that the investigator contact the sponsor or its designee if possible to discuss the particular situation, before breaking the blind. Telephone contact with the sponsor or its designee will be available 24 hours per day, 7 days per week. In the event the blind is broken, the sponsor must be informed as soon as possible. The date and reason for the unblinding must be documented by the IWRS, in the appropriate section of the case report form (CRF), and in the source document. The documentation received from the IWRS indicating the code break must be retained with the subject's source documents in a secure manner.

Subjects who have had their treatment assignment unblinded should continue to return for safety and immunogenicity evaluations, but will be withdrawn from study vaccine administration (see Section 10.2).

6. DOSAGE AND ADMINISTRATION

During the main study, each subject will receive doses of study vaccine or placebo at 4 time points according to randomization, on Weeks 0, 12, 24, and 48, administered by IM injection into the deltoid. Subjects eligible and consenting for the late boost vaccination will receive an additional dose of Ad26.Mos4.HIV in combination with bivalent gp140 or placebo at Week 192 -4 weeks/+ 4 months (ie, approximately 3 years after the 4th vaccination of the primary vaccination series).

For visits with only one injection (ie, at Week 0 and 12), preferably the deltoid of the non-dominant upper arm is used. When 2 injections are to be given at one visit (ie, at Week 24, 48 and late boost vaccination), it is required to use a different deltoid for each injection. Two injections in the same deltoid are allowed only if medically indicated.

For information on vaccination windows, see Section 9.1.2. If a subject cannot be vaccinated within the allowed window, then that vaccination should not be administered. However, if the window is missed due to a study pause (see Section 11.9), vaccination will be assessed on a case-by-case basis, upon discussion between sponsor and investigator. If a subject misses more than one study vaccination, he/she will be withdrawn from further study vaccination (see Section 10.2).

Table 3: Description of Interventions					
Test articles	Ad26.Mos4.HIV	Clade C gp140 with aluminum phosphate	Clade C gp140 + Mosaic gp140 with aluminum phosphate*	gp140 HIV bivalent vaccine*	Placebo
Description	See Section Vaccine Information.				
Dose/delivery (0.5 mL injection)	5x10 ¹⁰ viral particle (vp)	250 mcg Clade C gp140, mixed with aluminum phosphate adjuvant (0.425 mg aluminum)	125 mcg Clade C gp140 + 125 mcg Mosaic gp140, mixed with aluminum phosphate adjuvant (0.425 mg aluminum)	80 mcg Clade C gp140/75 mcg Mosaic gp140/ aluminum phosphate adjuvant (425 mcg aluminum)	0.9% saline
Frequency	Week 0, 12, 24, 48, and Week 192** (if applicable)	Week 24 and 48	Week 24 and 48	Week 192** (if applicable)	Week 0, 12, 24, 48, and Week 192** (if applicable)
Delivery method	IM in deltoid	IM in deltoid	IM in deltoid	IM in deltoid	IM in deltoid
Delivery instructions		Refer to the St	udy Procedures Mai	nual for details.	

^{*} The dosage of DP in the gp140 HIV bivalent vaccine (late boost vaccination) is identical to the dosage of DP in the co-administered separate gp140 formulations (main study). However, there has been a change of unit for the reported gp140 concentration from mg/mL glycoprotein to mg/mL protein. This will not impact the dose strength of gp140 in the vial or administered to the participants in the late boost extension, compared to the main study, but the gp140 concentration will be expressed in protein instead of glycoprotein in the specification. Consequently, 125 mcg Clade C gp140 and 125 mcg Mosaic gp140 of glycoprotein correspond with 80 mcg Clade C gp140 and 75 mcg Mosaic gp140 of protein, respectively.

7. TREATMENT COMPLIANCE

Subjects will receive doses of study vaccine or placebo at 4 or 5 time points administered by IM injection by qualified study-site personnel at the study sites.

The date and time of each study vaccine administration will be recorded in the CRF.

8. PRESTUDY AND CONCOMITANT MEDICATION

Prestudy medication administered up to 30 days before the screening visit will be recorded in the CRF at screening. In case a subject received an experimental vaccine more than 12 months prior to the Day 1 visit (Vaccination 1) and is determined to be eligible, administration of this experimental vaccine will be recorded in the CRF. For participants that consent to receive the late boost study vaccination, any COVID-19 vaccination must also be recorded at screening, regardless of how long before screening the vaccination took place.

Concomitant medication must be recorded in the CRF throughout the study from the signing of the ICF to the final main study visit at Week 72 and from the day of late boost vaccination until 28 days thereafter, if applicable. Beyond these time windows, only concomitant therapies given in conjunction with an SAE or in conjunction with AESIs of TTS will be collected. In addition, any chronic or recurrent use of immunomodulators/suppressors, oral or parenteral corticosteroids (see

^{**} The late boost vaccination is to be administered at Week 192 -4 weeks/+4 months, ie, approximately 3 years after the 4th vaccination of the primary vaccination series.

below), any allowed vaccination and/or any HIV prevention medication and any COVID-19 vaccination should be recorded in the CRF.

Use of any experimental medication (including experimental vaccines other than the study vaccine) during the main study is disallowed. Vaccination with any licensed vaccine within the 14 days prior to or after any dose of study vaccine or placebo is prohibited. However, if a vaccine is indicated in a post-exposure setting (eg, rabies or tetanus), it must take priority over the study vaccine. Subjects who enter the LTE phase are allowed to use any experimental medication during the LTE phase, irrespective of them receiving the late boost vaccination, except for:

- studies with investigational HIV vaccines or other investigational HIV prevention which could be determined to interfere with HIV vaccine response in this study (ie, CD4-Ig depleting Env-specific Abs), which are disallowed and studies with experimental immunomodulators/suppressors which are disallowed from signing of the ICF appendix for the late boost vaccination until the end of the study or would need prior sponsor approval if the subject will not receive the late boost vaccination.
- Vaccination with COVID-19 vaccines that have been either licensed or authorized for emergency use (eg, EUA, EUL, or similar program) must take priority over the study vaccine. The interval between late boost study vaccination and administration of a recombinant viral vectored COVID-19 vaccine or a live attenuated COVID-19 vaccine should be at least 28 days. The interval between study vaccination and administration of other types of COVID-19 vaccines (eg, mRNA vaccines, protein-based vaccines) should be at least 14 days.
- For participants planning to receive the late boost study vaccination, concomitant participation in an interventional study with COVID-19 vaccines is not allowed.

Study subjects can receive medications, such as acetaminophen, non-steroidal anti-inflammatory drugs, or antihistamines as needed, although their use must be documented and use of these medications as routine prophylaxis prior to study vaccination is discouraged.

Chronic or recurrent use of:

- Immunomodulators/suppressors, eg, cancer chemotherapeutic agents
- Oral or parenteral corticosteroids, eg, glucocorticoids

is an exclusion criterion for the main study (Section 4.2), and these medications are prohibited during the main study. During the LTE phase, use of these medications is discouraged, except when required by the medical condition of the subject, and each use should be reported during clinical visits. In case a subject uses or is planning to use these medications at the time of the late boost vaccination, it should be discussed with the sponsor on a case-by-case basis if this subject is allowed to receive the late boost vaccination. Ocular and topical steroids are allowed, as well as inhaled steroids for the treatment of pulmonary conditions.

The sponsor must be notified in advance (or as soon as possible thereafter) of any instances in which prohibited therapies are administered.

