11.2. Analysis Populations

The safety population will consist of all subjects who received at least one dose of study vaccine, and for whom any post-dose data is available.

The immunogenicity population will consist of all subjects who received at least one dose of study vaccine, and who have immunogenicity data from at least one evaluable post-dose blood sample.

The per protocol immunogenicity population will consist of all randomized and vaccinated subjects for whom immunogenicity data are available, excluding subject samples with major protocol deviations expecting to impact the immunogenicity outcomes (for example missed vaccinations, natural infections, etc).

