### **2.3.2. Per-Protocol Immunogenicity Analysis Set**

The per protocol immunogenicity (PPI) population consists of all subjects who have received at least the first three vaccinations, according to the protocol-specified vaccination schedule (+/- 2 weeks), have at least one measured post-dose blood sample collected and were not diagnosed with HIV during the study. Samples taken after Week 48 from subjects in the PPI population who missed the 4th vaccination or did not receive the 4th vaccination in the protocol-specified time window (+/- 2 weeks) will be excluded from the analysis.

The analysis of the immune responses will be performed on the per protocol immunogenicity population.

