#### 4.3. Concomitant Medications

The analysis of concomitant medications will be using the WHO drug dictionary as provided in the clinical database.

Based on their start and stop date, concomitant therapies will be reported in each period during which they were applied.

If a concomitant therapy record misses components of its start and/or stop dates (Day and/or month and/or year):

- In case of partial start or stop dates, the concomitant therapy records will be allocated to periods using the available partial information, without imputations. If, for example, only month and year are available, these will be compared to the month and the year of the periods, and the concomitant therapy record will be allocated to the period(s) where these date parts match.
- In case of a completely missing start date, the concomitant therapy will be considered as having started before the trial.
- In case of a completely missing end date, the concomitant therapy will be considered as ongoing at the end of the trial/cut-off date.

Concomitant therapies will be tabulated by post-dose phase. There will be special attention to Acetaminophen, NSAIDs or Antihistamines to identify medication that can mask local or systemic solicited events in the 8 days after the vaccinations and to systemic glucocorticosteroids during the whole study duration for possible influence on the immunogenicity results. Systemic glucocorticosteroids will be flagged in the overall CM listing. Subjects taking PrEP during the study will be listed.

Concomitant medication taken during the LTE will be listed.

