**6.4. Handling of Missing and/or Invalid Immune Response Data**

Analysis will be carried out on the available data, no imputation will be done for missing samples. BAMA and ICS unreliable values should be excluded from the analysis: those records will be flagged in the SDTM dataset.

LLOQs by assay/test are listed in section 6.5. Values below LLOQ or LOD will be handled as follows:

- Calculation of Geomean (humoral response except ADCP) and median (cellular response):
  - o values < LLOQ are imputed =LLOQ/2
  - o values = LOD are imputed =LLOQ/2

For ADCP only:

- o values < LOD are imputed =LOD/2

- Calculation of fold increases from baseline:
  - o values <LLOQ are imputed =LLOQ
  - o values =LLOQ are imputed = LLOQ

For ADCP only:

- o values < LOD are imputed =LOD

Values above the upper limit of quantification (ULOQ) will be handled as follows:

- Calculation of geomean and median:
  - o Values>ULOQ are imputed=ULOQ.
- Calculation of fold increases from baseline:
  - o Values >ULOQ are imputed with ULOQ

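### PrEP use is recorded and users are listed, but no rule flags or removes their TZM-bl results, so drug in serum could be counted as neutralising antibody

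*Protocol*

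**What the plan says.** **What may be taken.** During the main study, Protocol Section 8 bars experimental products: "Use of any experimental medication (including experimental vaccines other than the study vaccine) during the main study is disallowed". In the long-term extension (LTE) it bars "studies with investigational HIV vaccines or other investigational HIV prevention which could be determined to interfere with HIV vaccine response in this study", with a separate restriction on experimental immunomodulators. Neither sentence reaches a licensed PrEP product, and use is expected to be documented: "any allowed vaccination and/or any HIV prevention medication and any COVID-19 vaccination should be recorded in the CRF".

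**What the SAP does with the record.** Section 4.3 says "Subjects taking PrEP during the study will be listed". The same paragraph singles out "systemic glucocorticosteroids during the whole study duration for possible influence on the immunogenicity results", so the plan accepts that a medication can distort immunogenicity, but it attaches no such purpose to PrEP.

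**Who and what is analysed.** Under SAP 2.3.2, subjects need the first three vaccinations on schedule and must "have at least one measured post-dose blood sample collected and were not diagnosed with HIV during the study". PrEP is not a criterion. Protocol 11.2 removes samples affected by major protocol deviations, but taking a drug that is not prohibited is not a deviation. SAP 6.4 analyses the available data and adds one validity exclusion: "BAMA and ICS unreliable values should be excluded from the analysis: those records will be flagged in the SDTM dataset".

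**How TZM-bl is scored.** In SAP 6.5 the readout is ID50. LLOQ is 20 for the Clade B panel and 10 for the Clade C panel, and the responder rule is a titre above LLOQ. ELISA and ADCP, by contrast, require a 3-fold rise when baseline is at or above the limit.

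**The concern.** A virus neutralisation assay reports a titre when infection falls in the presence of the subject's serum. An antiretroviral carried in that serum can also reduce infection, and the readout alone does not separate the two causes. The documents do not describe this mechanism; it is general reasoning about what such an assay measures.

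Followed exactly, the plan would count a drug-affected sample as neutralising antibody, including in a placebo recipient. Because the responder rule ignores baseline, a subject already on PrEP at baseline could be a responder at each visit tested. A drug effect need not be strain-specific, so it could also look like breadth.

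The endpoint at stake is Env-specific neutralising antibody, titre and breadth, which Protocol 2.1 makes secondary for the main study, the LTE and the late boost. A false value can also carry forward. Under SAP 6.5, footnote b, Week 28 titres against two Clade C viruses decide which samples meet the wider panel at Week 52, and Week 52 titres decide what is assayed at Week 72.

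**Working it through.** **The plan's own figure.** There is none for TZM-bl. The only sample-size figure (Protocol 11.3) concerns binding antibody: 80% power for a 1.85-fold difference, SD 0.4 log10, about 90 against 22 evaluable. It reproduces. The standard error is 0.4 × √(1/22 + 1/90) = 0.0951, and log10(1.85)/0.0951 = 0.2672/0.0951 = 2.808. Then 2.808 − 1.960 = 0.848, which gives power 0.802. It is used here only for its group sizes.

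**Does any rule catch a PrEP sample?**
- Prohibited medication (Protocol 8): no, licensed PrEP is not covered.
- Per-protocol set (Protocol 11.2, SAP 2.3.2): no PrEP criterion.
- Unreliable values (SAP 6.4): BAMA and ICS only.
- Responder rule (SAP 6.5): above LLOQ, with no baseline comparison.
- PrEP-specific action (SAP 4.3): a listing.

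**Illustration of size.** Inputs from the documents: n = 25 planned placebo, about 22 in Group 1, about 90 in Group 2; LLOQ 10 or 20; values below LLOQ set to LLOQ/2 for geometric means (SAP 6.4). Assumptions not in the documents: one PrEP user in the group, whose own true titre is below LLOQ, and a false titre T of 100 to 500.

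Change in responder rate = 100/n. Ratio of geometric means = (T ÷ (LLOQ/2))^(1/n). The other subjects' titres cancel, so only the affected subject's own true titre matters.

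| Group | n | Responder rate | GMT ratio, LLOQ 20 | GMT ratio, LLOQ 10 |
|---|---|---|---|---|
| Placebo | 25 | +4.0 points | 10^(1/25) = 1.10 to 50^(1/25) = 1.17 | 20^(1/25) = 1.13 to 100^(1/25) = 1.20 |
| Group 1 | 22 | +4.5 points | 10^(1/22) = 1.11 to 50^(1/22) = 1.19 | 20^(1/22) = 1.15 to 100^(1/22) = 1.23 |
| Group 2 | 90 | +1.1 points | 10^(1/90) = 1.03 to 50^(1/90) = 1.04 | 20^(1/90) = 1.03 to 100^(1/90) = 1.05 |

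**If the user has a real response.** Take a true titre of 50 and the same T. The ratio is (T/50)^(1/n): 2^(1/22) = 1.03 to 10^(1/22) = 1.11 in Group 1, and 2^(1/90) = 1.01 to 10^(1/90) = 1.03 in Group 2. The responder rate does not move, because that subject is already above LLOQ.

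**Gating.** The wider Week 52 panel needs a Week 28 titre above 500 against MW965.26 or above 50 against 97ZA012.12. Week 72 testing needs a Week 52 titre above 50 or above 10 against the same viruses, each for its own virus. A false titre at Week 28 or 52 could pass these cut-offs. A true non-responder who starts PrEP only after Week 52 would not be tested at Week 72.

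**The case against.** The strongest reply is that the interference step lies outside the documents. They give no drug level, no residual activity at assay dilutions and no false titre, and a null effect is possible. This stands as a limit on size. It does not remove the gap, since the plan names a neutralisation assay, foresees PrEP use and says nothing about combining them.

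Several further points stand:
- Enrolment requires low HIV risk (Protocol 4.1, criteria 11 and 12), so users may be few. Randomisation should spread them at similar rates, leaving mainly chance imbalance between groups.
- TZM-bl is outside the geometric mean ratios and tests in SAP 6.3, which cover ELISA, ADCP and ELISpot. The SAP's magnitude-breadth plots cover ELISA and BAMA, although Protocol 11.4 also mentions such curves for neutralising antibody.
- SAP 6.5 leaves the final assay framework to the data presentation specification (DPS). A control could sit there or in the Laboratory Manual; neither was available for this review.
- SAP Section 1 says outputs up to Week 72 will not be repeated, so a main-study correction is more than a wording change.
- The BAMA and ICS exclusion is a record-level validity flag. Its silence on TZM-bl does not by itself show an oversight.

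A reader might infer that each PrEP user becomes a responder to every virus in any arm, for example adding 100/12 = 8.3 points among 12 late-boost placebo subjects (48 at 3:1). The documents do not support that. All late-boost subjects were vaccinated earlier and may already exceed LLOQ, the Week 52 and Week 72 testing is titre-gated, and the SAP names no late-boost time point for TZM-bl.

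**Conclusion.** The gap is real and modest. Licensed PrEP is allowed by absence of a prohibition rather than by an explicit statement; its use is recorded, and no analysis rule handles it for the one assay where it could mimic a response. If interference occurs, one affected true non-responder shifts the responder rate by 4.0 points in placebo, 4.5 in Group 1 and 1.1 in Group 2. A vaccinee with a real titre changes the geometric mean only slightly and the responder rate not at all.

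These figures rest on an assumed single user and an assumed false titre of 100 to 500. They are not estimates of bias in this trial. The documents do not show that reported neutralising-antibody results are inflated, or that the regimen comparison is compromised. The binding-antibody primary endpoint and the SAP 6.3 comparisons are unaffected. This is a cheap improvement to a secondary, descriptive analysis.

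**What to change.** In SAP 6.4:
- Flag TZM-bl samples drawn during recorded HIV-prevention medication use, or within a window after use that the assay laboratory states. Apply the missing-date conventions already in SAP 4.3.
- Exclude flagged samples from TZM-bl geometric means, fold changes and responder rates, unless a laboratory control shows no drug effect. If such a control exists, cite it.
- Report the number excluded by group and visit, and give a sensitivity table with them included.
- Apply the rule to any LTE or late-boost TZM-bl testing.
- Check the main-study TZM-bl results already reported against the PrEP listing, including whether a flagged titre admitted a sample to the gated Week 52 or Week 72 tests. Rerun only if a user is found.

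Binding-antibody and T-cell results from these subjects stay in. The cost is SAP wording, one flag derived from data already collected, one extra table and the loss of a few TZM-bl values. A main-study rerun would be additional work.
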